### 7 STUDY INTERVENTION DISCONTINUATION AND PARTICIPANT DISCONTINUATION/WITHDRAWAL

#### 7.1 DISCONTINUATION OF STUDY INTERVENTION

Discontinuation from drug or placebo administration does not mean discontinuation from the study, and remaining study procedures should be completed as indicated by the study protocol. All patients are expected to complete the treatment course unless they experience an SAE that is thought to be related to the study drug, die, are discharged early, or withdraw early from the study.

#### 7.2 PARTICIPANT DISCONTINUATION/WITHDRAWAL FROM THE STUDY

Participants are free to withdraw from participation in the study at any time upon request. An investigator may discontinue or withdraw a participant from the study if any clinical AE, laboratory abnormality, or other medical condition or situation occurs such that continued participation in the study would not be in the best interest of the participant

The reason for participant discontinuation or withdrawal from the study will be recorded on the Case Report Form (CRF). Subjects who sign the informed consent form and are randomized but do not receive the study intervention may be replaced.

#### 7.3 LOST TO FOLLOW-UP

A participant will be considered lost to follow-up if he or she is unable to be contacted by the study site staff within 2 weeks of the 90-day follow-up visit.

The following actions must be taken if study personnel are unable to contact participant for follow-up:

- Before a participant is deemed lost to follow-up, the investigator or designee will make every effort to regain contact with the participant (where possible, 3 telephone calls and, if necessary, contact with PCP). We will also screen obituaries and check the EMR for potential deaths.
- Should the participant continue to be unreachable, he or she will be considered to have withdrawn from the study with a primary reason of lost to follow-up.

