## 1 PROTOCOL SUMMARY

### 1.1 SYNOPSIS

Title:	Subarachnoid hemorrhage and soluble epoxide hydrolase inhibition: a phase 1b trial
Study Description:	Soluble epoxide hydrolase (sEH) is the metabolizing enzyme of epoxyeicosatrienoic acids (EETs), which may play a role in reducing neuroinflammation and regulating cerebral blood flow after subarachnoid hemorrhage (SAH). We hypothesize that pharmacologic inhibition of the sEH enzyme is safe and will result in increased EETs availability at the neurovascular unit, and a measured increase in the EET/DHET ratio in the serum and cerebrospinal fluid. This study is a double-blind, placebo-controlled, phase 1b randomized trial to evaluate the safety and of GSK2256294, an inhibitor of soluble epoxide hydrolase, in patients with aneurysmal SAH.
Objectives:	Primary Objective: Determine the safety of administration of GSK2256294 in patients with aneurysmal SAH. Secondary Objective: Determine the pharmacodynamics effect of administration of GSK2256294 in patients with aneurysmal SAH on reducing EETs metabolism and biomarkers of cerebrovascular inflammation and endothelial injury. Tertiary Objective: Provide preliminary estimates of clinical endpoints to inform the design of a larger trial
Endpoints:	Primary Endpoints: Determination of safety Secondary endpoints: 

1. Study days 7 and 10 serum EET/DHET ratios

2. Study days 7 and 10 cerebrospinal fluid (CSF) EET/DHET ratios

3. Study days 7 and 10 serum EPOME/DPOME ratios

4. Neuroinflammatory and endothelial injury biomarker levels from the blood and CSF at day 7 and day 10.

 Tertiary, exploratory endpoints: Clinical outcomes associated with SAH including neurologic status, disposition, vital status and incidence of delayed cerebral ischemia.  Up to 30 subjects will be randomized. Patients age 18 or above with confirmed ruptured will be approached to provide written informed consent. In order to be eligible to participate in this study, an individual must meet all of the following criteria: non-contrast CT with evidence of subarachnoid hemorrhage, and digital subtraction cerebral angiography or CT angiogram documenting the presence of

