## 2 INTRODUCTION

### 2.1 STUDY RATIONALE

SAH due to the rupture of an intracranial aneurysm is a life threatening medical emergency with a mortality of 25-40%. In survivors of the initial bleeding, endothelial injury and blood in the subarachnoid space induce an intense inflammatory response, leading to vessel wall thickening and caliber reduction over the first 10-14 days following the bleed. This inflammatory process may cause delayed cerebral ischemia (DCI). DCI is the clinical result of a complex neurovascular inflammatory response characterized by blood brain barrier breakdown, impaired blood vessel autoregulation, direct inflammatory injury, thrombosis, and cerebral edema. The ultimate result is decreased cerebral blood flow and altered neurovascular communications. The inflammatory and ischemic injury associated with DCI may result in long-term cognitive dysfunction and functional disability in >50% of survivors.

In an effort to prevent and treat DCI, patients with SAH require intensive care unit monitoring of hemodynamics and neurologic function for 10-14 days after the primary hemorrhage. Monitoring of the tone of intracranial blood vessels is routinely carried out daily with transcranial Doppler flow velocities, and cerebral angiography when indicated. Clinical deteriorations that are accompanied by signs of decreased cerebral blood flow are treated with blood pressure augmentation and/or intra-arterial vasodilators, with limited therapeutic effectiveness. The only recommended pharmacological therapy is the prophylactic administration of a 21-day course of the calcium channel blocker nimodipine.[1] There are currently no other effective therapies to directly target microvascular blood vessel dysregulation or neuroinflammation.

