### 5.4 STRATEGIES FOR RECRUITMENT AND RETENTION

The study population will draw from all adult patients admitted to the OHSU NSICU, part of a comprehensive stroke center certified by the American Heart Association and Joint Commission for Accreditation of Healthcare Organizations, with a catchment area including the state of Oregon, Southwest Washington and Northern California. Approximately 80-100 patients with aneurysmal SAH are admitted each year. All patients admitted with SAH have cerebral angiography or CT angiogram early after admission. Research personnel will review patients from the ICU census for eligibility on a daily basis.

To ensure completeness of follow up procedures, we will collect contact information from the patient, the patients legally authorized representative (LAR), the primary care provider (PCP), and the disposition location (facility) contact information at hospital discharge. The CareEverywhere electronic medical record network and obituary screening will be used to identify deaths.

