## TERTIARY ENDPOINT ASSESSMENTS

### **Discharge and Follow-up Assessments:**

At hospital discharge and 90-day follow-up, we will also measure objective clinical surrogate endpoints. The hospital discharge assessment will be abstracted from the patient medical record and obtained from patient interview. The 90-day follow-up assessment will be obtained from phone interview with the patient or their surrogate. We will collect the following information:

- **At Hospital Discharge:**
  - **Hospital length of stay**, in days
  - **New stroke on imaging:** We will review the last head CT or other brain imaging to detect the presence of a new area of cerebral infarction. We will define a cerebral infarction identified on hospital discharge that was not present on imaging between 24–48 hours after aneurysm occlusion, and not attributable to other causes such as surgical clipping or endovascular treatment. Hypodensities resulting from extraventricular drains or residual intraparenchymal hematomas will not be considered new strokes.
  - **Discharge disposition:** We will record the disposition from the hospital in one of the following categories: home, home with services, rehab, LTAC, SNF, hospice, death
  - **Modified Rankin Scale:** We will determine and record the mRS score from where 0 – no symptoms, 1 – no significant disability, able to carry out all usual activities despite some symptoms, 2 – slight disability. Able to look after own affairs without assistance, but unable to carry out all previous activities, 3 – moderate disability, requires some help, but able to walk unassisted, 4 – moderately severe disability, unable to attend to own bodily needs without assistance, and unable to walk unassisted, 5 – severe disability, requires constant nursing care and attention, bedridden, incontinent, 6 – deceased.
- **At 90-day follow up**
  - **Modified Rankin Scale**
  - **Extended Glasgow Outcome Scale (GOSE):** At 90 day follow up, we will determine the GOSE based on a structured interview of 19 questions detailed in the variable list and assessment tools. We will record the GOSE on a scale of 1-8 where 1 – deceased, 2 – vegetative state, 3 – low severe disability, 4 – upper severe disability, 5 – low moderate disability, 6 –upper moderate disability, 7 – low good recovery, 8 – upper good recovery.

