## 9.2 SAMPLE SIZE DETERMINATION

The total sample size was selected *a priori* based on the need to evaluate and describe the safety profile of the study drug in this patient population.

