#### 9.4.2 MISSING VALUES

Study investigators will monitor the study to maximize completion of data collection and samples. Every effort will be made to retain subjects to follow up. Patterns of missing data will be evaluated for the presence of informative missingness or if missing data are missing completely at random or at random.

---

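### Unreachable patients are searched for deaths only, so 90-day scores are missing mainly in survivors and the death share among scored patients is biased upward

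*Combined protocol and SAP*

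**What the plan says.** - **Source of the 90-day scores.** The discharge and follow-up assessments (Section 8, tertiary endpoints) state: "The 90-day follow-up assessment will be obtained from phone interview with the patient or their surrogate". Both scales contain death, as mRS 6 and GOSE 1.
- **Search for unreachable patients.** Section 5.4: "The CareEverywhere electronic medical record network and obituary screening will be used to identify deaths". Section 7.3 repeats this for patients who do not respond: "We will also screen obituaries and check the EMR for potential deaths". It also asks for three telephone calls where possible and contact with the primary care provider if necessary.
- **Patients still unreachable.** Section 7.3: "he or she will be considered to have withdrawn from the study with a primary reason of lost to follow-up".
- **Missing data.** Section 9.4.2: "Patterns of missing data will be evaluated for the presence of informative missingness". No method follows for what to do if it is found.
- **Analysis.** Section 9.4.4 summarizes tertiary endpoints by mean, median, standard deviation and range, with no denominator rule, bounds or sensitivity analysis.
- **Use.** Section 3 (tertiary objective) says the trial is not powered for these endpoints, but that they will inform sample sizes for larger studies.

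**The concern.** The search can move a patient out of the missing group in only one way, by finding a death. Information that the same search may turn up about a living patient has no stated use, and that patient becomes a withdrawal. Whether a 90-day score exists therefore depends on the outcome itself. A summary restricted to patients with a score keeps the deaths that were found and loses unreachable survivors from the denominator.

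The stake is the tertiary objective. A mortality figure that is too high, carried into the planning of a later trial, makes that trial look able to succeed with fewer patients than it needs. Section 9.1 lists no separate 90-day mortality endpoint, although the synopsis mentions vital status, so among the listed 90-day endpoints death enters only through the two scales. Adverse-event recording ends at 28 days or discharge, whichever is sooner (Section 8.6.4). Later deaths therefore depend on the 90-day contact and this search.

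**Working it through.** The plan gives no loss rate, expected 90-day outcome or power, so there is no figure of its own to reproduce. On sample size, the synopsis says "Up to 30 subjects will be randomized" and Section 9.2 says "The total sample size was selected *a priori* based on the need to evaluate and describe the safety profile".

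**Inputs**
- m, true 90-day mortality: 25% to 40%. Section 2.1 calls SAH "a life threatening medical emergency with a mortality of 25-40" percent. This is a background figure, used here as a range.
- u, share unreachable: 5%, 10% or 20% (assumed), taken as equal in survivors and in deaths not already known.
- s, share of unreachable deaths that the search finds: 50%, 80% or 100% (assumed).
- h, share of deaths already known from the hospital or a surrogate: 0 or 70% (assumed).
- Found deaths are scored mRS 6 / GOSE 1 and other lost patients have no score (inferred).

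**Death share among scored patients**

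Missing survivors: sm = (1 − m)·u. Missing deaths: dm = m·(1 − h)·u·(1 − s). Observed death share = (m − dm)/(1 − dm − sm).

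| m | u | s = 1 | s = 0.5, h = 0 |
|---|---|---|---|
| 25% | 5% | 0.25/0.9625 = 26.0% (+1.0) | 0.24375/0.95625 = 25.5% (+0.5) |
| 25% | 10% | 0.25/0.925 = 27.0% (+2.0) | 0.2375/0.9125 = 26.0% (+1.0) |
| 25% | 20% | 0.25/0.85 = 29.4% (+4.4) | 0.225/0.825 = 27.3% (+2.3) |
| 40% | 5% | 0.40/0.97 = 41.2% (+1.2) | 0.39/0.96 = 40.6% (+0.6) |
| 40% | 10% | 0.40/0.94 = 42.6% (+2.6) | 0.38/0.92 = 41.3% (+1.3) |
| 40% | 20% | 0.40/0.88 = 45.5% (+5.5) | 0.36/0.84 = 42.9% (+2.9) |

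The other combinations of s and h fall between these columns. The bias is upward in every case.

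**Who is missing.** The survivor share of missing scores is sm/(sm + dm). With h = 0 it is 100% at s = 1, 88% to 94% at s = 0.8, and 75% to 86% at s = 0.5 (for example 0.06/0.08 = 75% at m = 40%, u = 10%).

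**Against sampling error.** √(0.25·0.75/30) = 7.9 points and √(0.40·0.60/30) = 8.9 points. With 15 per arm these become 11.2 and 12.6 points.

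**Mean mRS.** Take m = 25%, u = 20%, s = 1, and observed survivors averaging 2.5 (assumed). The mean among scored patients is (0.25·6 + 0.60·2.5)/0.85 = 3.53. If lost survivors also average 2.5, the true mean is 1.5 + 0.75·2.5 = 3.38, so the summary looks too bad. If they average 5, it is 1.5 + 1.5 + 0.15·5 = 3.75, so the summary looks too good.

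**Effect on later planning.** Assume a 30% relative reduction in mortality, 80% power and two-sided 0.05, with n = [1.96·√(2p̄q̄) + 0.842·√(p₁q₁ + p₂q₂)]²/(p₁ − p₂)². Then n per arm is 466 for 25% but 377 for 29.4%, and 244 for 40% but 199 for 45.5%.

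**The case against.** The plan has real safeguards. Contact details are collected from the patient, the legally authorized representative, the primary care provider and the discharge facility, and a surrogate may give the interview, so losses at one site over 90 days may be few. Mortality is part of the primary safety review, and all deaths are listed (Section 9.4.3), with the safety population defined in Section 9.3. Known deaths can therefore already be set against all dosed patients. Reasons for withdrawal are summarized (Section 9.4.1), so lost patients stay identifiable. Discharge mRS and disposition are separate endpoints. The loss rates above are assumed, and 25-40% is not an expected mortality for consented patients. All of this stands, and it keeps the matter small. None of it says how the 90-day scales are summarized when patients are lost.

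A reader might infer three stronger things that the documents do not support:
- **That mean or median mRS/GOSE, or poor outcome, leans toward death.** The direction depends on how disabled the lost survivors are, and the mean-mRS example goes both ways.
- **That scores are missing almost only in survivors.** This depends on the yield of the search, which is not stated. Unreachable deaths that the search misses would also be missing.
- **That the comparison between arms is biased.** This would arise mainly if loss or mortality differed by arm, and nothing in the documents shows that.

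**Conclusion.** The asymmetry holds. Deaths can be found without contact, survivors cannot be scored without it, and no analysis rule corrects for this. The firm consequence is limited to the proportion dead among patients with a 90-day score. It is too high by about 1 to 2.6 points at 10% unreachable and 2.3 to 5.5 points at 20%, for mortality of 25-40%.

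This rests on three assumptions: the loss rates, the scoring of found deaths as mRS 6 / GOSE 1 (implied by the scales but not written), and equal reachability before the search. The direction would reverse only if unknown deaths were more than 1/((1 − h)(1 − s)) times as likely as survivors to be unreachable. With s = 0.5 and h = 0, that is more than twice as likely.

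The bias is smaller than sampling error at N = 30. It is nonetheless systematic, avoidable, and present in figures meant for planning. Severity is low, since the endpoints are tertiary, descriptive and unpowered.

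**What to change.** **Section 7.3.** Use the EMR, CareEverywhere and primary-care contacts already planned to record the last date known alive as well as any death. Keep lost patients in the analysis set, with lost to follow-up as a status of its own, instead of coding them as withdrawn.

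**Section 9.4.4.**
- State that a death by day 90 found by the search is scored mRS 6 / GOSE 1.
- Report 90-day death over all dosed patients, with an explicit category for vital status or score unknown.
- Show good-outcome proportions on mRS and GOSE with best-case and worst-case bounds (all unknowns good, all unknowns poor), plus a version using the discharge mRS already collected.

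For illustration, take 30 dosed patients with 8 known deaths and 3 unreachable. Scored patients alone give 8/27 = 29.6%. Over all dosed patients the bounds are 8/30 = 26.7% and 11/30 = 36.7%. If the EMR shows all three alive at day 90, the answer is 26.7% with no range.

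**Cost.** One CRF field, a small extra table, a few lines of text, and a range instead of a single figure when patients are lost. There is no added patient burden.

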## 8 STUDY ASSESSMENTS AND PROCEDURES

### 8.1 SCREENING, CONSENT, AND RANDOMIZATION

**Screening:** Research coordinators will survey the NSICU census on a daily basis to determine which patients are potentially eligible for enrollment. Patients who have cerebral angiography demonstrating ruptured intracranial aneurysm who satisfy the inclusion/exclusion criteria will be approached to provide informed consent. For women of childbearing potential, baseline urine pregnancy test will be performed at admission as part of the standard of care. If not already performed as part of standard medical care, liver function tests will be sent to determine subjects' baseline liver function.

**Consent:** We have developed a written consent to be reviewed and signed by the study participant or surrogate decision making. The recruitment process may take place in-person or by phone. A phone script is attached with this submission. Either the PI, coinvestigators or research staff will explain the objectives, risks and benefits of the study to the patient. We will allow adequate time to answer questions and address concerns.

Some patients will not be able to provide informed consent due to incapacity. Legally authorized surrogate decision makers will be approached to provide consent in these scenarios. There will be no financial compensation or incentive provided to study participants. Study candidates must sign the informed consent form before any study-specific tests or procedures are performed.

**Enrollment/randomization:** Eligible patients are defined as participants meeting all inclusion criteria and none of the exclusions and who have provided a written informed consent. Participants must be screened, consented, and enrolled in the study within 48 hours of admission to the OHSU NSICU. Participants will be randomized as described above. All participants who complete the informed consent process will be assigned a study identification number. Numbers will be assigned in consecutive order starting with the number 100. This number will be followed with another two-digit number representing the randomization sequence starting at 01. Participants will be referenced by the study identification number.

### 8.2 BASELINE EVALUATION

Baseline subject evaluation and testing will be performed in conjunction with routine intensive care unit treatment and monitoring. Data will be collected from the medical record or patient/surrogate interview.

- **Patient Demographics:** Ethnographic characteristics (age, sex, race/ethnicity, weight, height, BMI), level of education, and detailed contact information for follow-up

- **Characteristics of present illness:** Hunt and Hess Score, Fisher grade, location of aneurysm, surgical vs interventional treatment (completed or planned) and Glasgow Coma Scale (GCS) will be collected at the time of randomization.
- **Baseline Physiologic Data:** The first laboratory results and vital signs obtained at the time of ICU admission will be recorded, and detailed in the variable list in section 12. We will also collect details about history of preexisting medical comorbidities using the Charlson Comorbidity Index Score, screening for tobacco use, and targeted questions about neurologic history. A baseline EKG will be performed as part of the standard of care, and reviewed for evidence of conduction abnormalities or acute myocardial ischemia.
- **Admission medications:** Selected classes of medications administered from the time of ICU admission to randomization will be recorded. We will also record selected classes of home medications the patient may have been taking prior to hospitalization.

### 8.3 STUDY DRUG ADMINISTRATION SCHEDULE

The investigational pharmacy will maintain blinding, labeling and dispensing to healthcare providers of the study drug as described above. The first dose of study drug will be administered immediately after randomization. Subsequent doses will be administered daily in the morning for a total of 10 days. The preferred route of administration is orally, but patients with SAH are often neurologically compromised and unable to safely swallow. A suspended formulation will be administered via the orogastric or nasogastric route for patients deemed unsafe to swallow.

### 8.4 SAFETY ASSESSMENTS

#### 8.4.1 DAILY ASSESSMENTS

Daily assessments will be performed beginning on the randomization day (day=1), and on subsequent study days that subjects receive study drug (days 2-10). The randomization day will be defined as the time from randomization to the next 6:59 AM. All subsequent study days will be defined as a 24-hour window between 7:00AM and 6:59 AM the following day. Study staff will perform daily assessments from data collected from the medical record as part of patients' routine intensive care unit treatment and monitoring, or by patient interview. These include:

- **Vital Signs:** every four hour vital signs including blood pressure from noninvasive and arterial sources, heart rate, body temperature, and the presence of absence of mechanical ventilation;
- **Cardiac Monitoring:** daily QTc interval, and the presence of cardiac arrhythmias on continuous EKG monitoring.
- **Intake and Output:** total fluids administered and total drain and urine output;
- **Laboratory Assessments:** serum sodium, blood glucose, BUN, creatinine, hematocrit, peripheral white blood cell count;
- **Neurologic Assessments:** GCS, MCA transcranial Doppler velocities and Lindegaard ratios, and headache severity;
- **Concomitant medications:** Daily administration of selected classes of hospital administered concomitant medications will be reviewed for all study subjects during the first 10 days.

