### **Pharmacokinetics and product metabolism**

In human and animal studies, the oral bioavailability of GSK2256294 was generally high, indicating good absorption, low plasma clearance and a half-life of 20-30 hours. Steady state was achieved within 6-8 days after daily repeat dosing in humans.[12] GSK2256294 has low to moderate protein binding, high passive permeability, and a moderate volume of distribution. Structural information on GSK2256294 metabolism in humans following both single and repeat oral doses in both healthy volunteers and obese smokers indicated GSK2256294 was the major drug related component in human plasma with biliary and urinary metabolites being formed by either oxidation with or without subsequent glucuronidation and N-demethylation. Similar metabolites were detected in human and nonclinical hepatocytes.

In vitro data indicated limited potential for GSK2256294 to be a perpetrator of cytochrome P450-mediated drug interactions. Population-based physiologically based pharmacokinetics model simulations, evaluating the risk of an interaction between GSK2256294 and a strong CYP3A4 inhibitor, predicted a moderate increase (3.2 fold) to the mean systemic exposure of GSK2256294 when administered together. Co-administration of strong inhibitors and inducers of CYP3A4 has been recommended to be prohibited.

GSK2256294 inhibited the human breast cancer resistance protein and organic anion transporting polypeptide 1B1 in vitro, suggesting the potential for drug interactions with statins that have their disposition modulated by these transporters. However, a physiologically based pharmacokinetic population based drug-drug interaction modelling simulation between GSK2256294 and sensitive substrates (including rosuvastatin) has predicted the clinical interaction risk to be negligible (<1.05 fold). Hence monitoring of adverse events is recommended with the concomitant use of GSK2256294 with statins.

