### **Pharmacodynamics and Dose Finding**

The inhibitory effect of GSK2256294 on exogenous deuterium-labeled EETs was estimated in an ex vivo assay in healthy volunteers and otherwise healthy overweight to moderately obese smokers following single doses of 2-20mg, and following 14 days of once daily repeat dosing at 6mg and 18mg.[12] The sEH activity was evaluated by the formation of 14,15 dDHET, corrected for non-sEH mediated hydrolysis and subsequently the % inhibition of sEH activity was defined. >95% enzyme inhibition was observed for up to 48 hours following a single 10mg dose. >98% enzyme inhibition was observed to be sustained for up to 48 hours following 14 days of daily administration.

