#### 9.4.3 ANALYSIS OF THE PRIMARY ENDPOINT

Safety will be assessed by clinical review of all relevant parameters including vital signs, laboratory values, adverse events, serious adverse events, disease related events, and mortality. Unless specified otherwise, the safety analyses will be conducted for the safety population.

Summary tables and listings will be provided for all reported adverse events, defined as adverse events that start on or after the first administration of study drug. The reported adverse event term will be assigned a standardized preferred term.

Adverse events will be summarized based on the number and percentage of patients experiencing the event. In the event a patient experiences repeat episodes of the same adverse event, then the event with the highest severity grade and strongest causal relationship to study treatment will be used for purposes of incidence tabulations. Tabular summaries will be provided for all adverse events, the relationship to study drug treatment the maximum severity grade, action taken, and whether the event qualified as SAE or not.

Daily safety laboratory test results will be summarized in a descriptive manner by calculating the mean, standard deviation, median, and range. Directional shifts (comparing baseline grade with worst post-baseline grade) will be analyzed using standard shift tables. The shift table will present directional shifts from baseline to above or below the laboratory standard normal range using the maximum increase and/or decrease observed throughout the course of treatment/observation.

Vital signs will be summarized in a descriptive manner by calculating the mean, standard deviation, median, and range in the same manner described for laboratory values.

All deaths will be reported in a patient listing, which will include the primary cause of death and the number of days between the date of the last dose of study drug and death.

---

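### Section 8.4.1 can be read as ending the daily safety assessments when study drug stops, leaving patients taken off drug for harm with the fewest days in the worst-value laboratory tables

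*Combined protocol and SAP*

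**What the plan says.** Section 8.4.1 sets the daily assessments for the randomization day (Day 1) "and on subsequent study days that subjects receive study drug (days 2-10"). They cover four-hourly vital signs, "daily QTc interval, and the presence of cardiac arrhythmias on continuous EKG monitoring", fluid balance, six laboratory tests, GCS, transcranial Doppler and headache severity. In the same list, concomitant medications are reviewed for every subject over the first 10 days, with no dosing condition.

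Section 7.1 says that stopping drug is not leaving the study and that "remaining study procedures should be completed as indicated by the study protocol". It allows for early stopping because of a related serious adverse event, death, early discharge or withdrawal.

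Section 9.3 puts anyone with a single dose in the safety population. Section 9.4.3 summarizes daily laboratory values and vital signs descriptively, and builds laboratory shift tables "using the maximum increase and/or decrease observed throughout the course of treatment/observation". Section 3 makes the between-group comparison of the daily laboratory values part of the primary safety objective, and adds a description of daily headache severity.

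On timing, Section 8.3 states: "Subsequent doses will be administered daily in the morning for a total of 10 days". Section 8.4.1 states: "All subsequent study days will be defined as a 24-hour window between 7:00AM and 6:59 AM the following day". Section 2.2 reports "low plasma clearance and a half-life of 20-30 hours".

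**The concern.** Safety is the primary objective, and the measured values come from the daily assessments. If those assessments follow dosing and not the calendar, the amount of data per patient depends on tolerance of the drug. A patient stopped for a related serious event has fewer days in which a worst value can be found, and can appear in the shift table as unshifted because nobody recorded the later values. The daily means for later days would also describe only patients still taking drug. Either effect can hide harm in the patients most likely to show it. If related-event stops are more frequent on active drug, the distortion runs toward no difference between arms.

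A separate and lesser matter is that systematic measurement ends with Day 10 even for patients who complete dosing, while drug and enzyme inhibition persist beyond that.

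**Working it through.** The plan has no figure of its own to reproduce here: Section 9.2 gives no calculation, and the safety analysis is descriptive. The check compares the sections and then does two short calculations.

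**1. Which reading governs after an early stop?**
- Section 8.4.1 states a dosing condition and adds a bracketed day range. The bracket may be the calendar window, or it may be the range within which the condition applies.
- Section 7.1 points toward continuing, but only as the protocol indicates. For these items that leads back to 8.4.1.
- The concomitant-medication item in 8.4.1 is worded without a dosing condition, so the section uses both forms.
- The Schedule of Activities (Section 11) is given only as an attachment and is not in the text available. It could settle the point.

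The text therefore supports two readings.

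**2. Days lost on the literal reading.** With the last dose on Day k, days assessed = k and days lost = 10 − k.

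| Last dose | Days assessed | Days lost |
|---|---|---|
| Day 3 | 3 of 10 | 7 |
| Day 4 | 4 of 10 | 6 |
| Day 5 | 5 of 10 | 5 |
| Day 7 | 7 of 10 | 3 |

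On the calendar reading, days lost = 0 for a patient still in hospital.

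**3. Drug remaining when the Day 10 window closes.** Inputs: half-life 20 to 30 h (Section 2.2); a Day 10 morning dose (8.3); window closing at 6:59 AM the next day (8.4.1), so about 24 h or less after that dose. Assuming first-order elimination, fraction remaining = 0.5^(t / half-life).
- 24 h: 0.5^(24/20) = 0.435; 0.5^(24/30) = 0.574
- 48 h: 0.5^(48/20) = 0.189; 0.5^(48/30) = 0.330

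Section 2.2 also reports more than 95% inhibition for up to 48 h after a single 10 mg dose, which is the trial's dose. After repeat dosing, more than 98% "enzyme inhibition was observed to be sustained for up to 48 hours following 14 days of daily administration"; those cohorts took 6 mg and 18 mg, so applying that figure to 10 mg for 10 days is an extrapolation.

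Under a five-half-life convention, which is not in the documents, washout takes 5 × 20 = 100 h to 5 × 30 = 150 h, or 4.2 to 6.3 days. Subtracting the roughly one day already covered leaves about 3.2 to 5.3 days without scheduled measurement.

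**The case against.** The strongest reply is that Section 7.1 already answers the concern. It separates stopping drug from leaving the study, and the bracketed days in 8.4.1 can be the calendar window. That reading is reasonable and may be the intended one. A reader might infer that data are certainly lost after an early stop; the documents do not establish that, least of all with the Schedule of Activities unseen. What stands is that the operative sentence carries a dosing condition and 7.1 does not clearly override it.

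Second, few patients may be affected. Of the reasons in 7.1, death, discharge and withdrawal generally end inpatient data anyway, so the issue is mainly stops for a related serious event. That is correct, but those are the patients a safety study most needs to measure.

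Third, Section 8.6.4 records adverse events until 28 days or discharge, whichever is sooner, so a recognized arrhythmia, laboratory abnormality or headache can still be captured. This stands, and it limits the damage. It does not supply systematic values in both arms, which Sections 3 and 9.4.3 call for.

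Fourth, a reader might infer that closing at Day 10 biases the comparison toward no effect. It does not: the cut-off applies equally to both arms and limits the period described. Section 2.2 puts steady state at 6 to 8 days, so Days 8 to 10 already observe it, and levels fall afterwards.

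Fifth, a reader might conclude that daily collection should run to Day 16 to cover five half-lives. The documents do not support making that a requirement. Onset may be up to 3 days before admission (5.2) and enrollment up to 48 hours after it (8.1), so Day 1 falls 0 to 5 days after the bleed, Day 10 at 9 to 14 days and Day 16 at 15 to 20. Section 2.1 describes intensive monitoring for 10 to 14 days after the hemorrhage, so daily values may not exist by then. Follow-up ending at discharge would also observe sicker patients for longer.

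**Conclusion.** The point holds as an unresolved conflict between Sections 8.4.1 and 7.1 with a real consequence on one of its two readings. On the literal reading, an early stopper loses 10 − k of the 10 assessment days (6 of 10 for a last dose on Day 4) while staying in the safety population and the worst-value laboratory shift tables. On the calendar reading nothing is lost through Day 10. The documents give no expected number of early stops, so the overall effect cannot be sized; with up to 30 patients, a few could matter.

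The consequence concerns the laboratory shift tables and the laboratory and vital-sign summaries. Section 9.4.3 names no QTc summary and no vital-sign shift table, so no distortion of those analyses can be claimed, although the QTc and headache data would be missing as well.

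The Day 10 cut-off is a limitation of scope. Some 44% to 57% of drug remains when the window closes, on first-order elimination and the stated half-life, and more than 95% inhibition is reported to 48 h after a single 10 mg dose. The conclusions assume that the Schedule of Activities does not already set a fixed or later window.

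**What to change.** In Section 8.4.1, replace "and on subsequent study days that subjects receive study drug (days 2-10" and its closing bracket with: *and on study Days 2-10, or until hospital discharge or death if sooner, for every dosed subject, whether or not study drug is given that day*. Reconcile this with Section 7.1 and the Schedule of Activities so that all three state one window.

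In Section 9.4.3, build the laboratory shift tables and the laboratory and vital-sign summaries over that same window.

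State as a limitation that systematic measurements stop about 24 h after the last dose, while drug and inhibition persist. Values already in the chart after Day 10 may be tabulated descriptively, separately from Days 1-10.

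The cost is protocol wording plus a few extra days of chart abstraction for early stoppers. Section 8.4.1 draws mainly on routine intensive-care records, with some items by patient interview. Observation will still end early for patients who are discharged or die before Day 10.
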